2.2.6 Last assessment

A last assessment analysis visit will be created as the last available postbaseline assessment with a nonmissing value.

The last assessment will be created for the following parameters:

- BPDAI total and activity score
- IGA-BP
- Itch NRS 24-hour average and worst scores
- ABQOL, DLQI and EQ-5D-5L questionnaires
- GTI AIS and CWS
- Numeric parameters of safety lab, vital signs and ECG

For PD parameters, a last assessment analysis visit will be created per treatment period as the last available post-TPnB assessment with a nonmissing value in the treatment period. Assessments during the follow-up phase will be considered in the selection of the last assessment of the preceding treatment period.

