ABQoL=Autoimmune Bullous Disease Quality of Life questionnaire; AE=adverse event; BP=bullous pemphigoid; BPDAl=Bullous Pemphigoid Disease Area Index; CR=complete remission; DLQI=Dermatology Life Quality Index; ECG=electrocardiogram; eCRF=electronic case report form; EDV=early discontinuation visit; EFG=efgartigimod PH20 SC; efgartigimod PH20 SC=efgartigimod for SC administration coformulated with rHuPH20; EoTP=end-of-treatment period (visit); F1/F2=follow-up visits 1 and 2; GTI=Glucocorticoid Toxicity Index; GTI-AIS=GTI Aggregate Improvement Score; GTI-CWS=GTI Cumulative Worsening Score; GTI-SL=GTI Specific List; IGA-BP=Investigator Global Assessment of Bullous Pemphigoid; NA=not applicable; NRS=numerical rating scale; OCS=oral corticosteroids; PBMC=peripheral blood mononuclear cell; PD=pharmacodynamics; PK=pharmacokinetics; PR=partial remission; QoL=quality of life; rHuPH20=recombinant human hyaluronidase PH20; SC=subcutaneous; SoA=schedule of activities; UNS=unscheduled visit; W=week

Note: Assessments indicated in gray font will only be recorded on the ARGX-113-2009 eCRF and not on the ARGX-113-2010 eCRF.

^a The baseline visit will occur on the same day as the EoTP visit of ARGX-113-2009. All baseline assessments will be performed before administration of efgartigimod PH20 SC. Assessments do not need to be repeated if performed as part of the ARGX-113-2009 EoTP visit.

^b Day X applies when efgartigimod PH20 SC is initiated (refer to Section 6.3). Efgartigimod PH20 SC treatment will be started on day X, which can be the same day as the day the relapse is confirmed. Subsequent visits will be relative to day X, except for the EoTP visit that will take place 48 weeks after baseline for all participants.

- ^c Participants who stopped receiving efgartigimod PH20 SC after rollover but before protocol amendment 2 is effective will enter the observation period with visits every 8 weeks. Efgartigimod PH20 SC will be initiated at the investigator's discretion or if relapse occurs during the study. Participants who initiate efgartigimod PH20 SC must follow the SoA in [Table 2](#) as of day X (refer to [Section 6.3](#) for more details).
- ^d Visit F1 (EoTP + 4 weeks) is only applicable for participants receiving efgartigimod PH20 SC at week 48.

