- ^e When a participant permanently discontinues IMP and/or is withdrawn from the study during the treatment period, study sites should attempt to perform the EDV within 7 days after the participant's final IMP administration and safety follow-up visits 4 and 8 weeks after the participant's final IMP administration. If a participant is withdrawn from the study during the observation period, refer to the SoA in [Table 1](#).
- ^f A UNS may be performed if the participant has (or suspects they have) new BP lesions or other issues requiring site staff intervention, such as notable weight change. At these visits, the investigator will determine whether efgartigimod PH20 SC therapy must be started/resumed and will decide which assessments to conduct based on the purpose of the UNS. If relapse occurs, IGA-BP, BPDAl, and itch NRS assessments must be performed.
- ^g A brief physical examination should be performed instead of a complete examination if the participant had a complete physical examination ≤ 4 weeks before day X.
- ^h Brief physical examinations, GTI, and QoL will be assessed every 16 weeks relative to the last performed assessment. WOCBP will have urine pregnancy tests every 4 weeks relative to the last performed assessment.
- ⁱ If the time point of the assessment does not coincide with a planned on-site visit, the assessment should be performed at the next on-site visit.
- ^j Weight must be measured only if the participant is being administered OCS.
- ^k The urine pregnancy test is only applicable for WOCBP. The pregnancy test at the F2 visit is only applicable for participants on efgartigimod PH20 SC at EoTP/EDV.
- ^l Efgartigimod PH20 SC will be administered once weekly, [REDACTED] (on days 1 and 8 of treatment) and weekly maintenance doses of 1000 mg will be used. Refer to [Section 6.3](#) for more information and to [Section 6.5](#) for information about (self-)administration. Week 48 is the last time point that participants may receive doses of efgartigimod PH20 SC.
- ^m Participants and/or their caregivers will be invited to receive at least 1 refresher training course for efgartigimod PH20 SC (self-)administration. Training may continue or be repeated until the participant (or caregiver) is considered capable of performing the (self-)administration.

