6.3. Assignment to Study Intervention

The following general principles apply to all participants. These principles apply to the specific situations described in Section 6.3.1 and Section 6.3.2 unless mentioned otherwise.

- Efgartigimod PH20 SC can be initiated until week 45 to ensure a minimum of 4 weeks of treatment.
- Efgartigimod PH20 SC should be initiated without concurrent OCS if the participant's BP disease status permits it, according to the investigator's clinical judgment.
- Localized lesions should be treated with TCS before concurrent OCS treatment is considered, if possible.
- If there is no improvement in the participant's BP disease status and additional BP therapy is required while receiving efgartigimod PH20 SC, concurrent OCS treatment may be initiated according to the investigator's clinical judgment. Recommendations for OCS therapy initiation and tapering are provided in Section 6.9.1.
- As described in Section 6.9.2, rescue therapy will be tapered or discontinued in participants who received it in ARGX-113-2009. IMP will be permanently discontinued if the investigator considers it not to be in the participant's best interest to taper or discontinue rescue therapy.

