All nonmissing postbaseline values on or after the first administration of IMP in ARGX-113-2010 and up to and including 60 days after the last IMP administration before the assessment will be considered when deriving the worst-case analysis visit. This may include unscheduled assessments, assessments not selected for the analysis visit and assessments during the follow-up phase.

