- 9) Time to relapse:
 - Start date is the first day with status CDA, CR or PR in the treatment period (or observation phase)
 - End date is:
 - the start date of first relapse after having or achieving CDA, CR or PR
 - the end date of the study (end date of last phase), if no relapse
 - Time to relapse (in days) = end date - start date + 1
- 10) For participants with relapse, severity of (first) relapse will be calculated as the BPDAl total score at the onset of relapse (use the first available nonmissing BPDAl total score in the interval of relapse) minus the BPDAl total score at the preceding visit (use the most recent preceding visit for which a nonmissing BPDAl total score is available). Severity of relapse will be categorized as <0 , $0- <10$, $10- <20$, $20- <30$, or >30 .

	Statistical Analysis Plan	
ARGX-113-2010	Final analysis	Final 1.0 of 29APR2025

The following endpoints will be derived **overall**:

- 11) Changes and percent changes from study baseline will be calculated for BPDAI activity and total score.
- 12) Changes from study baseline will be calculated for itch NRS 24-hour average and worst scores.
- 13) C-GTI: Composite Glucocorticoid Toxicity Index comprises the Aggregate Improvement Score (AIS) and the Cumulative Worsening Score (CWS). Details of AIS and CWS derivations are specified in appendix 9.1.
- 14) A total ABQOL score is calculated as the sum of all 17 items score 0 to 3 with higher score indicating worse condition. Missing items are imputed with the average score of the present items if at least half (9) of the items are present. The total score is rounded to the highest integer.
- 15) Changes from study baseline will be calculated for EQ-5D-5L VAS score, DLQI score and total ABQOL score.

4.1.3 *Presentation of results*

Efficacy results will be presented for the ROL analysis set, unless mentioned otherwise. For tables by analysis visit, only the study baseline and last assessment analysis visits will be shown. Other analysis visits will be included in listings.

A frequency tabulation will be created for the number and percentage of participants who achieved CROff at least once during the study (i.e., in any treatment period). The table will also present the number of participants who are evaluable for the endpoint at least once during the study. This number will serve as denominator for the percentage calculation. This table will be based on the SAF analysis set.

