In addition, for all pharmacodynamic endpoints, descriptive statistics of the actual values and percent changes from baseline will also include GM and GSD. GM and GSD of percent changes from baseline are calculated as $100X \{ \exp(\theta) - 1 \}$ where θ is respectively the arithmetic mean and arithmetic SD of a variable calculated as $\log(\text{aval}) - \log(\text{base})$. GM and GSD are not applicable for descriptive statistics of the absolute changes from baseline.

4.2.3 *Presentation of results*

The SAF analysis set will be used for the PD evaluation. For tables by analysis visit, only the TPnB and last assessment analysis visits in a treatment period will be shown. Results for treatment period 2 will only be presented if at least 10 participants have a post-TP2B PD assessment.

All pharmacodynamic endpoints will be summarized by means of descriptive statistics at each analysis visit of interest in a treatment period. Actual values, changes from TPnB and percent changes from TPnB will be tabulated. Descriptive statistics of the actual values and percent changes from TPnB will also include GM and GSD. GM and GSD are not applicable for descriptive statistics of the absolute changes from TPnB.

	Statistical Analysis Plan	
ARGX-113-2010	Final analysis	Final 1.0 of 29APR2025

Listings will be created for [REDACTED] and anti-BP antibodies results over time, based on the ROL analysis set. Listings will always show the non-imputed results.

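### The last-assessment rule has no on-treatment limit, so the by-visit efficacy-score and autoantibody tables give no identifiable on-treatment summary

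*SAP*

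**What the plan says.** For BPDAI, IGA-BP and itch NRS, SAP 2.2.6 states that "A last assessment analysis visit will be created as the last available postbaseline assessment with a nonmissing value". It names no phase, subperiod or maximum time since dosing. For PD parameters the last assessment is taken per treatment period, and the section adds: "Assessments during the follow-up phase will be considered in the selection of the last assessment of the preceding treatment period".

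The presentation sections then restrict what is shown. For efficacy, SAP 4.1.3: "For tables by analysis visit, only the study baseline and last assessment analysis visits will be shown". For PD, SAP 4.2.3: "For tables by analysis visit, only the TPnB and last assessment analysis visits in a treatment period will be shown". Other efficacy visits, and the autoantibody results over time, go to listings.

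On dosing, Protocol 1.3, Table 2 footnote l says: "Week 48 is the last time point that participants may receive doses of efgartigimod PH20 SC". The same table schedules BPDAI, IGA-BP, itch NRS and the autoantibodies at F1 (EoTP + 4 weeks, for those on efgartigimod at week 48) and at F2 (EoTP + 8 weeks). Protocol 8 makes F2 a visit for all participants.

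**The concern.** The secondary objective covers long-term efficacy with treatment and also durability of response. These are two questions. A score or antibody level at week 48 bears on the first, and one eight weeks after the last injection bears on the second. The by-visit tables offer one post-baseline row, and whether it answers one question or the other depends on whether the participant came back for follow-up.

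The row also gathers other kinds of value. The efficacy tables use the rollover set, so they include participants who stopped efgartigimod before amendment 2 and any who were never dosed. For a participant who was on efgartigimod at the end of ARGX-113-2009, study baseline is an on-drug value. If that participant also has F2 data, the tabulated change in score runs from on drug to off drug. (PD changes use the treatment-period baseline instead.) Quality-of-life and GTI measures are not scheduled at F1 or F2, so the same row label normally means week 48 or EDV in those tables.

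What is at stake is interpretation: a reader of these tables cannot find an on-treatment summary of disease scores or autoantibodies.

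**Working it through.** **The plan's own figure.** Treatment of 48 weeks plus follow-up of 8 weeks: 48 + 8 = 56 weeks, which agrees with the stated total of approximately 56 weeks (Protocol 4.1, SAP 1.2).

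**Days since last dose at follow-up.** Inputs from Protocol Table 2: weekly dosing; EoTP window ±7 days; F1 at EoTP + 28 ± 3 days; F2 at EoTP + 56 ± 3 days.
- Last dose at EoTP: F1 = 28 ± 3 = 25 to 31 days; F2 = 56 ± 3 = 53 to 59 days.
- Last dose at week 47: EoTP falls 7 ± 7 = 0 to 14 days later. F1 = 0 + 25 to 14 + 31 = 25 to 45 days; F2 = 0 + 53 to 14 + 59 = 53 to 73 days.

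**On-treatment assessments that the by-visit tables leave out when F2 data exist.** Assessments fall at 2, 4 and 8 weeks after the start and then every 4 weeks, with EoTP fixed: "Subsequent visits will be relative to day X, except for the EoTP visit that will take place 48 weeks after baseline for all participants". The latest start follows from Protocol 6.3: "Efgartigimod PH20 SC can be initiated until week 45 to ensure a minimum of 4 weeks of treatment".
- Start at week 0: weeks 2, 4, 8, 12, …, 48 = 13.
- Start at week 8: weeks 10, 12, 16, …, 48 = 11.
- Start at week 24: weeks 26, 28, 32, …, 48 = 7.
- Start at week 45: weeks 47, 48 = 2.

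**Participants who stopped before amendment 2 and never restarted.** With the stop at week s, F2 is 56 − s weeks after stopping. Assumed values: s = 24 gives 32 weeks; s = 40 gives 16 weeks. The documents do not give actual stop times.

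**Whether another rule closes the gap.** I found no other section that limits the last assessment. SAP 2.2.5 limits the worst-case visit to values "up to and including 60 days after the last IMP administration before the assessment will be considered when deriving the worst-case analysis visit", but it expressly allows follow-up assessments. With a last dose at EoTP, F2 at 53 to 59 days is within 60 days and would still be selected. SAP 4.3.3 leaves out observation- and follow-up-phase visits, but only in the immunogenicity tables.

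**Tables affected.** 14.2.1.10, .11, .12, .13 and .14 (five) plus 14.2.3.2 (one) = six. Table 14.2.3.1 follows the same PD rule and makes seven; its parameter is blacked out. In 14.2.3.2 a treatment period is left out when its baseline is below quantification or under 20 RU/mL (SAP 4.2.2), and period 2 appears only if at least 10 participants have data (SAP 4.2.3).

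**What cannot be calculated.** The shift in a tabulated mean depends on the share of participants with F2 data and on how far scores and antibodies move in the eight weeks off drug. The documents give neither.

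**The case against.** The strongest reply is that the choice is deliberate and defensible. SAP 2.2.6 says outright that follow-up samples count for PD. Durability of response is part of the objective. F2 is scheduled for everyone, and completing it defines study completion, so for completers the row is a coherent end-of-study value. There is no hypothesis test and no estimand. The remission, relapse and treatment-failure tables do not use this rule, and the remaining visits are listed. All of this stands. It is a reason to keep the off-drug value and to treat the matter as one of presentation. It does not supply the missing on-treatment row.

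Three stronger readings are tempting, and the documents do not carry them:
- A reader might infer that the row cannot be interpreted at all, or that change from baseline usually compares on drug with off drug. Both depend on F2 attendance, which is not given.
- A reader might take the 60-day limit in SAP 2.2.5 as evidence that the SAP separates on-drug from follow-up data elsewhere. That section admits follow-up values, and its limit would let F2 through.
- A reader might think the SAP has no usable on-treatment period because Off IMP begins one minute after the last dose. SAP Table 2 applies that boundary to participants with a subsequent Off IMP subperiod. For others, On IMP runs to the end of the day of the week 48 or EDV visit.

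It is also fair to say that the same sentence in 2.2.6 governs laboratory and vital-sign values. The point is confined to scores and autoantibodies because the safety cross-tabulations also carry a worst-case row. A single on-treatment row also would not by itself give the time course that the endpoint wording and table titles suggest.

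**Conclusion.** The point holds as a gap in presentation and should be fixed. For a participant dosed to week 48 with F2 data, the only post-baseline value in six named tables (seven with the redacted one) is taken about eight weeks off drug: 53 to 59 days after a dose at EoTP, up to 73 after a week-47 dose. Up to 13 scheduled on-treatment assessments are left to listings. Because others contribute on-drug, EDV, long-stopped or never-dosed values, no by-visit row is an identifiable on-treatment summary.

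This rests on the visit windows in Protocol Table 2 and on F2 data being present. A reader might go further and infer that the tables are biased against or in favour of efgartigimod. The documents do not support that, since the size and direction of any distortion are unknown. The primary adverse-event endpoints are not touched.

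**What to change.** In SAP 2.2.6, add a last on-treatment assessment for BPDAI, IGA-BP, itch NRS and the PD parameters in dosed participants. Define it as the last nonmissing post-baseline value (post-TPnB for PD) in the On IMP subperiod of SAP Table 2. For participants with no Off IMP subperiod, that subperiod already runs to the week 48 or EDV visit, so no new day limit is needed. A sentence stating which participants have an Off IMP subperiod, in particular early discontinuers with an EDV, would make the row reproducible.

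In SAP 4.1.3 and 4.2.3, tabulate this row with its n, per treatment period for PD. Keep the current last assessment as a separate row labelled as end of study, including follow-up, with n and the median and range of days since last IMP. Identify never-dosed participants by row or footnote. Do not borrow the 60-day limit from 2.2.5.

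Cost: SAP wording, one derived analysis visit, a days-since-last-IMP variable of the kind 2.2.5 already needs, and extra rows in six or seven tables, with the programming and validation that go with them. No new data are required.

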2.3 IMPUTATION AND ROUNDING RULES

2.3.1 Missing values

No imputation will be done of missing values (i.e., observed cases analysis).

2.3.2 Handling partially or completely missing dates in calculations

OCS administration start dates with partially missing data will be imputed as follows:

- Missing day will be imputed with first day of the month or start date of the first phase, whichever comes latest.
- Missing day and month will be imputed with 1JAN or start date of the first phase, whichever comes latest.
- Completely missing date will be imputed with start date of the first phase.

	Statistical Analysis Plan	
ARGX-113-2010	Final analysis	Final 1.0 of 29APR2025

OCS administration end dates with partially missing data will be imputed as follows:

- Missing day will be imputed with the last day of the month or the end date of the last phase, whichever comes first.
- Missing day and month will be imputed with 31DEC or the end date of the last phase, whichever comes first.
- Completely missing end date will be imputed with the end date of the last phase.

2.3.3 Values below or above a threshold

Safety values expressed as BQL or AQL will be imputed by the value of the quantification limit itself.

██████ values expressed as BQL or AQL will not be imputed.

For anti-BP180 and anti-BP230, see section 4.2.2.

Anti-drug antibodies (ADA) against efgartigimod: titer of positive ADA samples reported as 'negative titer', i.e. '<1' will be imputed by 1.

For all the above cases, listings will always present the reported (non-imputed) result.

2.3.4 Rounding

Variables will be rounded to the appropriate number of decimals at display level:

- OCS dose will be rounded to 0 decimals.
- BMI and percent changes from baseline will be rounded to 1 decimal.
- OCS dose per body weight will be rounded to 2 decimals.
- Safety laboratory results will be rounded to a maximum of 3 decimals.

2.3.5 Outliers

There will be no outlier detection. All measured values will be included in the analyses.

2.4 PRESENTATION OF RESULTS

2.4.1 Calculation of descriptive statistics and percentages

Descriptive statistics for continuous variables will include the number of nonmissing observations, arithmetic mean, standard deviation (SD), standard error (SE), median, minimum, Q1, Q3 and maximum.

Descriptive statistics for immunogenicity titer values will also include geometric mean (GM) and geometric standard deviation (GSD).

Mean, median, Q1, Q3, GM and GSD will be presented with one more decimal place than the reported values. SE and SD will be presented with two more decimal places than the reported values. Minimum and maximum will be presented with the same number of decimal places as the reported values.

Event-type safety data will be summarized by presenting the number and percentage of participants with an event, and the number of events. The denominator will be all participants in the PAS.

	Statistical Analysis Plan	
ARGX-113-2010	Final analysis	Final 1.0 of 29APR2025

For frequency tabulations and cross-tabulations, the denominator will be the number of participants with nonmissing values in the PAS. For tables where results are shown by analysis visit, the denominator will be the number of participants with nonmissing values in the PAS per analysis visit. For cross-tabulations of postbaseline results versus study baseline results, a ‘missing’ category will be shown for baseline results, if applicable, and included in the calculations of percentages.

Percentages will be presented with one decimal place.

	Statistical Analysis Plan	
ARGX-113-2010	Final analysis	Final 1.0 of 29APR2025

2.4.2 *Presentation of treatments*

The following treatment arm label will be used in displays in the ROL analysis set:

- Total

The following treatment arm label will be used in displays in the SAF analysis set:

- Total Efgartigimod PH20 SC

2.4.3 *Ordering in tables, listings, and figures*

In tables showing several parameters, each parameter will begin on a new page and parameters will be sorted alphabetically, within the parameter category if applicable.

Listings will be ordered by participant identifier and, if applicable, by phase/period/subperiod, analysis visit, and time point, unless specified otherwise.

	Statistical Analysis Plan	
ARGX-113-2010	Final analysis	Final 1.0 of 29APR2025

